9.2.3. Electrocardiogram

Triplicate ECGs will be performed at study approved facility at time points as indicated in the TIME AND EVENTS SCHEDULE. Additional monitoring of ECG may be done, if in the opinion of the investigator, this is clinically indicated or if needed as part of the cardiac events management plan (see Section 9.2.8.7). The mean of the triplicate ECGs need to be taken into account for decision making. The representative ECG parameters as indices are described below.

- Heart Rate
- QRS interval
- QTc interval
- QT interval
- U wave
- ST

- T wave
- PR interval

During the collection of ECGs, subjects should be in a quiet setting without distractions (eg, television, cell phones). Subjects should rest in a supine position for at least 5 minutes before ECG collection and should refrain from talking or moving arms or legs. If blood sampling or vital sign measurement is scheduled for the same time point as ECG recording, the procedures should be performed in the following order: ECG(s), vital signs, blood draw.

The triplicate ECGs should be performed approximately 2 minutes apart over 10 seconds.

Twelve-lead ECGs will be recorded at a paper speed of 25 mm per second until 4 regular consecutive complexes are available. ECG machines will record timings of ECG measurements.

ECGs will be digitalized with local review by the investigator for immediate safety assessment. Digital ECG data will be transmitted to a centralized ECG over-read service provider. Over-read of the ECGs will be transmitted back to the site within 72 hours.

In case of inconsistent results, a technical problem with the ECG or an incorrect application of the ECG leads should be ruled out. In case of any abnormal value, the ECG recording has to be repeated.

Any clinically relevant changes occurring from signing of ICF onwards until the subject's last study visit must be recorded in the Adverse Event Section of the eCRF.

9.2.4. Echocardiography

The cardiac monitoring requirements outlined in the protocol are critical and must be followed for all subjects. Repeated transthoracic echocardiography will be performed at study approved facilities to assess various echocardiographic parameters including LVEF at time points as indicated in the TIME AND EVENTS SCHEDULE. The screening assessment will serve as baseline value. Additional echocardiography may be done, if in the opinion of the investigator, this is clinically indicated or if needed as part of the cardiac events management plan (see Section 9.2.8.7).

Echocardiograms will be performed according to a standard protocol as described in the study manual. The same technique of echocardiography must be used for each assessment. A variety of echocardiographic parameters, including LVEF, will be quantitated and compared over time as an assessment of safety by a central reader. These measures aim to reduce variability and enhance the precision of the study results.

Any clinically relevant changes occurring from signing of ICF onwards until the subject's last study visit must be recorded on the Adverse Event Section of the eCRF.

9.2.5. Vital Signs

Systolic and diastolic blood pressure and pulse rate will be assessed with a completely automated device. Manual techniques will be used only if an automated device is not available.

Blood pressure and pulse rate measurements should be taken supine and preceded by at least 5 minutes of rest in a quiet setting without distractions (eg, television, cell phones).

Any clinically relevant changes occurring from signing of the ICF until the subject's last study visit must be recorded in the Adverse Event Section of the eCRF.

9.2.6. Hepatitis B Virus DNA

Reactivation of HBV has been reported in association with successful treatment of hepatitis C in subjects who are infected with the HBV or patients who have a history of being infected (ie, HBsAg negative and antiHBc or hepatitis B surface antibody positive). If the drug is administered to subjects who have a history of HBV infection, attention should be paid to the occurrence of signs or symptoms related to reactivation of HBV by monitoring results of HBV markers such as HBV DNA.

Hepatitis B virus DNA will be measured by PCR testing at the EOT Visit, or Treatment Withdrawal Visit, and may be evaluated any time when there is a significant increase in the AST or ALT levels. This only refers to subjects with antiHBc and/or antiHBs positive status at screening and not to subjects who have received HBV vaccine and are only antiHBs positive (See TIME AND EVENTS SCHEDULE). In case of need of treatment for reactivated HBV, subjects will permanently discontinue the study drugs and receive a standard of care for HBV infection at the investigator's discretion.

9.2.7. Physical Examination

To evaluate the subject's eligibility, a complete physical examination (including height, body weight, and body systems and, if considered necessary by the investigator based on the subject's past and present medical history, breast, genitals, or rectal examination) will be performed at screening. A targeted physical examination based on the medical history and overall clinical presentation (including body weight) will be performed at the other time points indicated in the TIME AND EVENTS SCHEDULE.

A complete physical examination includes the following: general appearance, eyes, ears, nose, throat, cardiovascular system, respiratory system, abdomen, and skin and mucous membranes. It does not include breast, genitals, or rectal examination unless considered necessary by the investigator based on the subject's past and present medical history. A neurologic and musculoskeletal examination as well as an examination of the lymph nodes will also be performed.

The height should be measured barefooted at the Screening Visit. To obtain the actual body weight, subjects must be weighed lightly clothed.

Any clinically relevant abnormalities occurring from signing of the ICF until the subject's last study visit must be recorded in the Adverse Event Section of the eCRF.

9.2.8. Management of Specific Toxicities

The safety monitoring and toxicity management plan described below takes into account the clinical safety data of AL-335, ODV, and SMV, target organs identified in nonclinical studies of AL-335, ODV, and SMV. Cardiac events and increased bilirubin are considered events of special interest for the 3- and 2-DAA combination programs. Photosensitivity is considered an event of clinical interest.

9.2.8.1. Rash (Including Photosensitivity Conditions)

Subjects should be informed that they should contact their doctor immediately when they notice any skin reaction. The skin reaction should be evaluated in the clinic the same day (if possible) or the next day.

Photosensitivity conditions fall under the general umbrella of rash events. However, photosensitivity reactions can be differentiated from other rash events by careful history taking and general physical examination. Photosensitivity skin reactions are typically triggered by prolonged or extreme exposure to sunlight or artificial light. These reactions may present as an exaggerated sunburn reaction, usually affecting areas exposed to light (typically the face, 'V' area of the neck, extensor surfaces of the forearms, and the dorsa of the hands). Photosensitivity reactions can be prevented by avoiding excessive sun exposure and by the use of sun protection measures.

All rash events should be captured in the Adverse Event Section of the eCRF. A separate Rash Page will be completed in case of a rash event. For rash events considered as potential photosensitivity reaction, a separate Photosensitivity Page will be completed.

Monitoring of the evolution of rash (including photosensitivity reactions) will be performed based on the grade (severity) of the rash (see Attachment 3). At the discretion of the investigator, additional visits and assessments can be performed. Management of rash will take into account the protocol-defined procedures outlined in Table 3.

Discontinuation of all study drugs should be considered if a photosensitivity reaction occurs and subjects should be monitored until the reaction has resolved.

WHO Grade	Rash Definition	Investigator Action
Grade 1 Rash	erythema	May continue intake of study drugs at
(with or without pruritus) ^{a,d}		the investigator's discretion.
		Blood tests for safety (recommended) can be done at the investigator's discretion.
Grade 2 Rash (with or without pruritus) ^{b,d}	diffuse, maculopapular rash, OR dry desquamation	May continue intake of study drugs at the investigator's discretion.
		Blood tests for safety (recommended) can be done at the investigator's discretion.
Grade 3 Rash ^d	vesiculation, moist desquamation, or ulceration OR any cutaneous event with one of the following: -elevations in AST/ALT >2×baseline value -fever >38°C or 100°F	Permanently discontinue the intake of SMV. AL-335 and ODV may be continued at the investigator's discretion. ^c Close monitoring is required to prevent progression of the rash.
	-eosinophils >1.00×10 ³ /µL -serum sicknesslike reaction	No rechallenge is allowed.
		Blood safety tests are mandatory.
		Referral to a dermatologist is required. At the discretion of the dermatologist a biopsy might be performed.
Grade 4 Rash ^d	exfoliative dermatitis, OR mucous membrane involvement, OR erythema multiforme major, OR	Permanently discontinue the intake of all study drugs.
	Stevens-Johnson Syndrome, OR necrosis requiring surgery.	No rechallenge is allowed.
		Blood safety tests are mandatory.
		Referral to a dermatologist is required.
K AOT	ansferase; ALT=alanine aminotransferase; OI	A biopsy is required.

Table 3:	Guidelines for Subjects Developing Rash Grade 1 to Grade 4
----------	--

Key: AST=aspartate aminotransferase; ALT=alanine aminotransferase; ODV=odalasvir; SMV=simeprevir; WHO=World Health Organization

^a In case the rash evolves from a Grade 1 to a higher grade, management of the rash should follow the guidelines indicated for Grade 2 or Grade 3 or 4 rash, respectively (see Attachment 3).

^b In case the rash evolves from a Grade 2 to a Grade 3 or 4 rash, management of the rash should follow the guidelines specified for Grade 3 or 4 rash (see Attachment 3).

^c Monotherapy with any of the study drugs is not allowed.

^d Determine if subject was adhering to the recommended sun-protective measures.

When safety blood samples are drawn as per the rash management guidelines, these should be processed by the local laboratory. The following parameters will need to be tested: AST, ALT, sedimentation rate, complete blood cell count (including hemoglobin, hematocrit, RBC count, WBC count, platelet count, neutrophils, lymphocytes, monocytes, eosinophils, and basophils), and creatinine. The values of the local laboratory assessments need to be transcribed in the eCRF by the study-site personnel.

NCT02993250

Clinical Protocol 64294178HPC2003 Amendment 5

The subject may be treated symptomatically until the rash resolves. Oral antihistamines (eg, cetirizine and levocetirizine) and/or topical corticosteroids may provide symptomatic relief but effectiveness of these measures has not been established. If systemic corticosteroids for longer than 24 hours are required for the treatment of rash, the study drugs need to be permanently discontinued. If the rash is considered to be most likely due to concomitant illness or nonstudy drugs, standard management, including discontinuation of the likely causative agent should be undertaken.

Dermatologist fees for evaluating subjects who experience a rash during the study will be reimbursed by the sponsor.

The following grades are based on the World Health Organization (WHO) Toxicity Grading Scale (see Attachment 1) with adaptations made by the sponsor.

Grade 1 Rash (With or Without Pruritus)

A Grade 1 rash is defined as **erythema**.

- Subjects may continue the intake of study drugs (at the investigator's discretion).
- An unscheduled visit may be performed at the investigator's discretion as soon as possible after the subject contacts the investigator to report the AE.
- Assessment of safety blood samples by the local laboratory is recommended. The values of the local laboratory assessments need to be transcribed in the eCRF by the study-site personnel.

Unscheduled visits may also be performed after the initial rash assessment at the investigator's discretion for appropriate follow-up until resolution of the rash. At these visits, safety blood samples can be taken at the investigator's discretion. For these and all subsequent local laboratory blood sample assessments, the values of the assessments need to be transcribed in the eCRF by the study-site personnel.

The subject should be advised to contact the investigator immediately if there is any worsening of the rash, if any systemic signs or symptoms appear, or if mucosal involvement develops. If appropriate, sun protection counseling should be provided.

In case the rash evolves from a Grade 1 to a higher grade, management of the rash should follow the guidelines indicated for Grade 2 or Grade 3 to 4 rash, respectively.

Grade 2 Rash (With or Without Pruritus)

A Grade 2 rash is defined as diffuse, maculopapular rash OR dry desquamation.

- Subjects may continue the intake of study drugs (at the investigator's discretion).
- An unscheduled visit for initial rash evaluation is required as soon as possible after the subject contacts the investigator to report the AE. If a visit is not possible, telephone contact with the subject should take place to collect information and to give advice on the necessary measures to be taken.

- Assessment of safety blood samples by the local laboratory is recommended. The values of the local laboratory assessments need to be transcribed in the eCRF by the study-site personnel.
- Referral to a dermatologist is optional but, when done, should occur preferably within 24 hours after the onset of the rash. The investigator should obtain a copy of the dermatologist's report for assessment of rash.

Unscheduled visits will also be performed after the initial rash assessment at the investigator's discretion for appropriate follow-up until resolution of the rash. At these visits, safety blood samples can be taken at the investigator's discretion. For these and all subsequent local laboratory blood sample assessments, the values of the assessments need to be transcribed in the eCRF by the study-site personnel.

The subject should be advised to contact the investigator immediately if there is any worsening of the rash, if any systemic signs or symptoms appear, or if mucosal involvement develops. If appropriate, sun protection counseling should be provided.

In case the rash evolves from a Grade 2 to a Grade 3 to 4 rash, management of the rash should follow the guidelines specified for Grade 3 to 4 rash.

Grade 3 or Grade 4 Rash

A Grade 3 rash is defined as a rash associated with:

- vesiculation, moist desquamation, or ulceration, OR
- any cutaneous event with one of the following:
 - elevations in AST/ALT >2×baseline value
 - fever $>38^{\circ}$ C or 100° F
 - eosinophils >1.00×10³/ μ L
 - serum sicknesslike reaction

Subjects will permanently discontinue SMV. AL-335 and ODV may be continued at the investigator's discretion. Close monitoring is required to prevent progression of the rash.

A Grade 4 rash is defined as:

- exfoliative dermatitis, OR
- mucous membrane involvement, OR
- erythema multiforme major, OR
- Stevens-Johnson Syndrome, OR
- necrosis requiring surgery

Subjects will permanently discontinue all study drugs. No rechallenge is allowed.

An unscheduled (on-site) visit including a safety laboratory evaluation is required for a Grade 3 or 4 rash as soon as possible after the subject contacts the investigator to report the AE.

Assessment of safety blood samples by the local laboratory is required on the day of initial rash evaluation and the day thereafter (Days 0 and 1). The values of the local laboratory assessments need to be transcribed in the eCRF by the study-site personnel. Referral to a dermatologist is required, preferably within 24 hours after the onset of the rash. A copy of the dermatologist report should be collected by the investigator.

A biopsy may be performed at the discretion of the dermatologist for Grade 3 rash and is required in case of a Grade 4 rash as soon as possible after the onset of rash. The investigator should obtain a copy of the dermatologist's report.

Appropriate management should be undertaken and subjects should be followed until resolution of the rash or until clinical stability is reached.

A complete summary of the guidelines for rash management is given in see Attachment 3.

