16.2.6. Country Selection

This study will only be conducted in Japan, where the intent is to launch the developed product.

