Attachment 3: Visit Schedule for Rash Management

This visit schedule summarizes the visits and assessments to be performed in case of rash. At the investigator's discretion, additional visits and assessments can be performed. Local laboratory blood sample assessments will be documented/collected as described in the text below.

	Grade 1 Rash	Grade 2 Rash	Grade 3 or 4 Rash
Day 0 ^a	 Study medication MAY be CONTINUED. Unscheduled visit (onsite) for initial rash evaluation may be performed at the investigator's discretion. Assessment of safety blood sample by local laboratory RECOMMENDED. 	 Study medication MAY be CONTINUED. Unscheduled visit (onsite) for initial rash evaluation REQUIRED. If a visit is not possible, telephone contact with the subject should take place to collect information and to give advice on the necessary measures to be taken. Assessment of safety blood sample by local laboratory RECOMMENDED. Referral to dermatologist OPTIONAL (preferably within 24 hours after onset of rash, if performed). 	 Grade 3: SMV MUST be permanently DISCONTINUED. AL-335 and ODV MAY be CONTINUED at the investigator's discretion. Close monitoring is REQUIRED to prevent progression of the rash. Grade 4: Study medication MUST be permanently DISCONTINUED. Rechallenge is NOT ALLOWED. Unscheduled visit for initial rash evaluation as soon as possible after the subject contacts the investigator to report the event REQUIRED. Assessment of safety blood sample by local laboratory REQUIRED. Referral to dermatologist REQUIRED (preferably within 24 hours after onset of rash). Biopsy REQUIRED for grade 4 rash (as soon as possible after onset of rash). Biopsy at the dermatologist's discretion for grade 3 rash.
Day 1			• Follow-up visit (on-

NCT02993250

Clinical Protocol 64294178HPC2003 Amendment 5

	Grade 1 Rash	Grade 2 Rash	Grade 3 or 4 Rash
			 site) REQUIRED. Assessment of safety blood sample by local laboratory REQUIRED.
Further Visits	 Appropriate unscheduled Follow-up Visits at the investigator's discretion until resolution of rash.^b At these visits, safety blood samples can be taken at the investigator's discretion. 	 Appropriate unscheduled Follow-up Visits at the investigator's discretion until resolution of rash.^b At these visits, safety blood samples must be taken. 	Appropriate follow-up REQUIRED until resolution of rash or until clinical stability is reached.

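### The Grade 3 rash fever limit pairs two unequal temperatures (38°C and 100°F) in a rule that stops simeprevir permanently; one value should be stated (minor correction)

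*Protocol*

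**What the plan says.** Section 9.2.8.1 of the Protocol grades rash and ties an action to each grade. A rash is Grade 3 on its appearance (vesiculation, moist desquamation or ulceration), or when any cutaneous event is joined by one item from a short list. That list covers a transaminase rise, raised eosinophils, a serum-sickness-like reaction and "fever >38°C or 100°F". One item is enough. The same temperature pair stands in Table 3 and in the running text under the Grade 3 or Grade 4 heading.

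The consequence of Grade 3 is fixed in three places:

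- The text of Section 9.2.8.1 says "Subjects will permanently discontinue SMV".
- Attachment 3 says "SMV MUST be permanently DISCONTINUED".
- Table 3 gives the same instruction and adds, in its Grade 3 row, "No rechallenge is allowed". It also makes safety bloods mandatory and dermatology referral required.

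Below Grade 3 the action is softer. For Grades 1 and 2, Table 3 says "May continue intake of study drugs at the investigator's discretion", and initial bloods are recommended. For Grade 2 the text says "Referral to a dermatologist is optional but, when done", it should preferably happen within 24 hours.

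**The concern.** A threshold given in two units should be one temperature written twice. Here it is two temperatures, and the rule can be read in two ways:

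- **As a unit conversion.** The limit is 38°C and the Fahrenheit figure is wrong.
- **As written, with the two figures as alternatives.** The limit is 100°F, and the Celsius figure does nothing, because every temperature above 38°C is already above 100°F.

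No other section settles it. The fever row of Attachment 1 is a separate severity scale, and it pairs 100.0°F with 37.7°C rather than 38°C.

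At stake is how a mild rash with a borderline temperature is handled. On one reading all three drugs may continue at the investigator's discretion. On the other, SMV must be stopped for good, with required bloods and referral. A mandatory and irreversible stop should not depend on which unit the reader looks at.

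**Working it through.** **Inputs.** 38°C and 100°F, from Table 3 and the text of Section 9.2.8.1, each applied as a strict greater-than. For comparison, the lower bound of Grade 1 fever in Attachment 1: 37.7°C, paired with 100.0°F.

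**Formulas.** F = C × 9/5 + 32 and C = (F − 32) × 5/9.

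**The plan's own pair.**

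- 38 × 9/5 + 32 = 100.4°F, not 100°F.
- (100 − 32) × 5/9 = 37.78°C, not 38°C.
- The two agree only after rounding to whole degrees (100.4 to 100; 37.78 to 38).

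**Width of the disputed band.** 38.0 − 37.78 = 0.22°C; 100.4 − 100.0 = 0.4°F.

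**Readings in the band, if temperature is read to 0.1°C (an assumption).**

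| Reading | In °F | Above 100°F? | Above 38°C? |
|---|---|---|---|
| 37.7°C | 99.86 | no | no |
| 37.8°C | 100.04 | yes | no |
| 37.9°C | 100.22 | yes | no |
| 38.0°C | 100.40 | yes | no |
| 38.1°C | 100.58 | yes | yes |

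Three readings are graded differently by the two figures.

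**If temperature is read to 0.1°F instead (an assumption).** 100.1°F (37.83°C), 100.2°F (37.89°C), 100.3°F (37.94°C) and 100.4°F (38.00°C) are above 100°F and not above 38°C. That is four readings. 100.0°F is above neither limit, and 100.5°F (38.06°C) is above both.

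**Check against Attachment 1.** 37.7 × 9/5 + 32 = 99.86°F, which the scale rounds to 100.0°F. So the protocol's own fever scale treats 100°F as lower than 38°C. It does not support the rash pair.

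**How often it could arise.** The protocol gives no figure from which to count misgraded subjects. A case needs a rash with no other Grade 3 feature, a temperature taken for that rash, a reading in the band, and a site that applies the Fahrenheit figure. Section 9.2.5 says "Systolic and diastolic blood pressure and pulse rate will be assessed" and lists no temperature. Section 16.2.6 says "This study will only be conducted in Japan". If sites there read in Celsius and apply only that figure (an assumption the protocol does not state), no reading is affected.

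**The case against.** The best case on the other side is that this is copy-editing. The pair agrees to the whole degree, so 100°F is probably a rounded companion to 38°C. Attachment 1 rounds its own pairs in the same way: 38.5°C stands beside 101.5°F, where exact conversion gives 101.3°F. About 40 subjects are planned, in one country where Celsius is likely to be the working unit.

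Neither reading leaves a subject unprotected. The literal reading stops SMV earlier. On the other reading, continuation is at the investigator's discretion, and Section 10.2 requires discontinuation whenever the investigator believes safety calls for it. Subjects are told to call at once if systemic signs appear, and Grade 2 already requires a visit or, failing that, a telephone contact.

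Most of this stands, and it sets the weight of the point. It does not remove the error, because these figures are the operative trigger of a mandatory stop and nothing in the protocol says that 100°F is rounded.

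Three stronger inferences are not supported:

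- **That all three places bar rechallenge at Grade 3.** Only Table 3 does. In the text of Section 9.2.8.1 and in Attachment 3, the bar follows the Grade 4 rule.
- **That bloods are merely recommended throughout Grade 2.** Attachment 3 says samples must be taken at further Grade 2 visits, so the contrast with Grade 3 is sharp only at the initial evaluation.
- **That a needless SMV stop would cost virologic response.** Section 3.2 notes three relapses in cohorts given AL-335 and odalasvir without SMV. Section 1.2 places them in genotype 1a, and Section 1.1.1 says almost all genotype 1 in Japan is 1b. They are no estimate of harm in this trial.

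**Conclusion.** The point holds as a minor error. The two figures are not the same temperature, the pair stands in both operative places, and the protocol does not say which governs. Between 37.78°C (exclusive) and 38.0°C (inclusive), a rash with no other Grade 3 feature is Grade 3 by one figure and not by the other, and Grade 3 means a mandatory permanent SMV stop.

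The size is very small: three possible readings at 0.1°C or four at 0.1°F, and none if only the Celsius figure is applied. All three counts rest on assumptions about how sites read temperature. At most, the recorded grade and the SMV decision for an individual rash could change. A reader might infer that subjects will be misgraded in number or that the safety results are compromised; the documents give no basis for either.

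**What to change.** State one threshold in Table 3 and in the Section 9.2.8.1 text. In place of "fever >38°C or 100°F", write: fever >38.0°C (>100.4°F). This treats the Fahrenheit figure as a rounded conversion.

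The sponsor should confirm that 38°C is intended, because against the literal reading the change raises the trigger of a safety stop by 0.22°C. If 100°F was intended, write >37.8°C (>100°F) instead. Since 37.8°C is itself rounded (it is exactly 100.04°F), the protocol should then say which unit decides.

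The cost is a wording change in two places. No procedure, visit or analysis is added.
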